10.2.3. Follow-up of SAEs

The Investigator will provide follow-up information regarding a reported SAE using the SAE form providing the results of relevant examinations, laboratory and diagnostic tests, and hospitalisation records as needed.

Investigators must follow subjects with AEs/SAEs until the event has resolved, the condition has stabilized, withdrawal of consent, subject is lost to follow-up or death OR until 30 days after the last dose of study drug, whichever occurs first. Ongoing treatment-related AEs/SAEs may be followed beyond the 30-day follow-up period if clinically indicated.

10.2.4. SAEs occurring after the 30-day safety follow-up period

After the 30 day follow-up period, any SAEs that are considered related to any study drug or protocol procedures will be captured in the e-CRF and reported to the Sponsor using the SAE form.

10.3. REPORTING OF STUDY TREATMENT OVERDOSE TO THE SPONSOR

An overdose of study drug (whether symptomatic or asymptomatic) is to be reported as an AE in the e-CRF.

For the purpose of this trial, an overdose will be defined as any study drug dose administration exceeding the subject's assigned dose of study drug (s) as per protocol recommendations.

In the absence of associated AE seriousness criteria, the overdose and associated non-serious AE, are reported only on the AE page of the e-CRF. **If the definition** of seriousness criteria **is met for any associated AE**, the SAE form must be also completed and transmitted to the Sponsor.

10.4. REPORTING OF PREGNANCY TO THE SPONSOR

Pregnancy occurring during the period between signing of the ICF but before any study treatment exposure is not to be reported to the Sponsor unless associated to an AE.

If pregnancy is suspected while the female subject is receiving study treatment, the study treatment(s) should be discontinued immediately until the result of the pregnancy testing is known. If pregnancy is confirmed, administration of study drug is to be discontinued immediately and the subject must be withdrawn from the study.

The Investigators must report to the Sponsor any on-treatment pregnancy of a female subject or a female partner of a male subject which occurs during study treatment and within the 30 days after the last dose administration of binimetinib or encorafenib and within the 6 months after the last dose administration of cetuximab.

On-treatment pregnancy (of female subject and female partner of male subject) must be reported to the Sponsor within 24 hours of the Investigator's knowledge using the investigational product pregnancy form.

Any pregnancy will be followed through to outcome, and the outcome must be reported to the Sponsor, including the infant's health status, using the pregnancy outcome report form.

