5.3. LIFESTYLE GUIDELINES

5.3.1. Contraception

Female subjects who are postmenopausal for at least 1 year or are surgically sterile for at least 6 weeks are considered to be of non-childbearing potential.

Female subjects of childbearing potential must agree to take appropriate precautions to avoid pregnancy from screening through 6 months after the last dose of cetuximab or through 30 days after the last dose of encorafenib or binimetinib, whichever is later.

Male subjects must agree to take appropriate precautions to avoid fathering a child and prevent exposure of seminal fluid to the partner from screening through 6 months after the last dose of cetuximab or through 90 days after the last dose of encorafenib or binimetinib, whichever is later.

The following methods are permitted under this protocol for use by the subject and his/her partner. These methods are listed below and should be communicated to the subjects and their understanding confirmed.

Methods that have been determined to be highly effective (i.e., can achieve a failure rate < 1% per year when used consistently and correctly) according to the CTFG 2014 (**Clinical Trials Facilitation Group**) include:

- Complete abstinence from heterosexual intercourse during the entire period of risk associated with the study treatments; the reliability of sexual abstinence should be evaluated in relation to the duration of the clinical trial and the preferred and usual lifestyle of the subject
- Combined (estrogen and progestogen containing) hormonal contraception associated with inhibition of ovulation:
 - Oral
 - Intravaginal
 - Transdermal
- Progestogen-only hormonal contraception associated with inhibition of ovulation:
 - Oral
 - Injectable
 - Implantable
- Intrauterine device (IUD)
- Intrauterine hormone-releasing system (IUS)
- Bilateral tubal occlusion
- Vasectomised partner (considered highly effective provided the vasectomized male has received medical assessment of surgical success and that the male is a female subject's sole sexual partner)

Acceptable birth control methods that result in a failure rate of more than 1% per year (CTFG 2014) include:

- Progestogen-only oral hormonal contraception, where inhibition of ovulation is not the primary mode of action
- Male or female condom with or without spermicide
- Cap, diaphragm or sponge with spermicide

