Asymptomatic absolute decrease of > 10% in LVEF compared to baseline and the LVEF is below the institution's LLN (e.g., a decrease of 60% to 48% is an absolute decrease of 12%)	Interrupt dosing of binimetinib and repeat evaluation of LVEF within 2 weeks. 
 If the LVEF recovers (defined as LVEF ≥ 50% or ≥ lower limit of normal (LLN) and absolute decrease ≤ 10% compared to baseline) ≤ 21 days, resume treatment at 1 reduced dose level^b of binimetinib after approval of the Sponsor's Medical Monitor. Monitor LVEF 2 weeks after resuming binimetinib, every 4 weeks for 12 weeks and subsequently as per protocol. If LVEF does not recover in ≤ 21 days, permanently discontinue binimetinib. Closely monitor LVEF until resolution or for up to 16 weeks.
Grade 3 – 4	Permanently discontinue binimetinib. Closely monitor LVEF until resolution or up to 16 weeks. Note: Copies of ECHO and/or MUGA scans could be requested for subjects to be available to the Sponsor for subjects with absolute decrease of >10% in LVEF compared to baseline and LVEF < 50% or LLN.
CK Elevation	
Grade 1-2	Maintain dose of encorafenib and binimetinib. Ensure subject is adequately hydrated. Closely monitor CK and serum creatinine. 
 If total CK ≥ 3 × ULN, measure CK isoenzymes and myoglobin in blood or urine.
Grade 3 > 5.0 - 10.0 × ULN without renal impairment (i.e., serum creatinine < 1.5 × ULN or 1.5 × baseline)	If asymptomatic, maintain dosing of encorafenib and binimetinib. Ensure subject is adequately hydrated. Monitor and measure isoenzymes and myoglobin in blood or urine and serum creatinine. If symptomatic (muscle pain/spasms/muscle weakness), maintain dosing of encorafenib and interrupt dosing of binimetinib until resolved to CTCAE Grade ≤ 1 and monitor closely, then: 
 If resolved in ≤ 21 days, maintain dose of encorafenib and resume treatment at 1 reduced dose level^b of binimetinib. If not resolved in ≤ 21 days, maintain dose of encorafenib and permanently discontinue binimetinib.

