8.3.7. Dermatologic Evaluations

Dermatologic evaluations will be performed at the site by the Investigator to monitor for the possible development of keratoacanthoma (KA) and/or squamous cell carcinoma (SCC), as these have been reported to occur with selective BRAF inhibitor treatment. This assessment can be done predose or postdose and will be performed at the time points specified in the Flowchart (please refer to the flow-chart corresponding to the current period: Main study or Study extension).

In case of occurrence of KA or SCC, subjects will undergo complete surgical excision of the skin lesion following institutional standards. The evaluation can be done by the dermatologist if clinically indicated.

It is recommended that dermatological examination should be performed every two months for up to 6 months following discontinuation of encorafenib.

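### Partner-pregnancy reporting (10.4) and the 30-day stop on AE/SAE follow-up (10.2.3) do not match the longer windows the protocol sets in 5.3.1 and Table 14

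*Protocol*

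**What the plan says.** **Partner pregnancy.** Protocol Section 10.4 covers female subjects and female partners of male subjects in one sentence. Beyond the treatment period it gives two limits: "within the 30 days after the last dose administration of binimetinib or encorafenib", followed directly by "and within the 6 months after the last dose administration of cetuximab". Section 5.3.1 asks men to avoid fathering a child for 6 months after cetuximab "through 90 days after the last dose of encorafenib or binimetinib, whichever is later". For women of childbearing potential, the oral-drug figure in 5.3.1 is 30 days.

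**Follow-up of ongoing events.** Section 10.2.3 ends required follow-up of an AE or SAE at resolution, stabilisation, consent withdrawal, loss to follow-up or death, "OR until 30 days after the last dose of study drug, whichever occurs first". Longer follow-up of treatment-related events is permitted but not required. In Table 14, the left ventricular dysfunction rows, which adjust binimetinib only, say "Closely monitor LVEF until resolution or for up to 16 weeks" after permanent discontinuation. The rows for other (non-retinal) eye disorders ask for ophthalmic monitoring until the event stabilises or resolves, with no day limit.

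**After day 30.** AE recording runs to 30 days after the last dose (Section 8.3.1). After that, Section 10.2.4 says that "any SAEs that are considered related to any study drug or protocol procedures will be captured", with no end date. Section 8.3.7 recommends that "dermatological examination should be performed every two months for up to 6 months following discontinuation of encorafenib".

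**The concern.** The protocol sets certain periods over which it wants an outcome avoided or an event watched, but Section 10 does not always require the resulting data for the same periods. A man can still be inside his contraception window when a partner's pregnancy is no longer clearly reportable. An unresolved LVEF fall can still be under the monitoring Table 14 asks for when its outcome no longer has to be followed as an AE.

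At stake are pregnancy-exposure outcomes and the description of reversibility. The SAP tabulates TEAEs by worst outcome and describes the maximum duration of AESIs (Section 15.2). It imputes the end date of an AE left ongoing to the data cut-off (Section 11.2.4). An event that recovers after required follow-up has ended could therefore be tabulated as unrecovered and, if it belongs to an AESI grouping, as lasting to the cut-off.

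**Working it through.** The plan states no figure to reproduce here; the check compares time windows.

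**1. Partner pregnancy**

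Inputs: 30 days and 6 months (Section 10.4); 90 days and 6 months (Section 5.3.1). Assumption: 6 months = 6 × 365.25/12 = 182.6 days. Let *g* be the number of days by which the last cetuximab dose precedes the last oral dose. All times below count from the last oral dose. The two reporting limits are read as alternatives.

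- Reporting ends at max(30, 182.6 − g).
- The male window ends at max(90, 182.6 − g).
- The gap is the second minus the first.

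| g (days) | Reporting ends | Male window ends | Gap (days) |
|---|---|---|---|
| 0 | 182.6 | 182.6 | 0 |
| 92 | 90.6 | 90.6 | 0 |
| 93 | 89.6 | 90 | 0.4 |
| 100 | 82.6 | 90 | 7.4 |
| 120 | 62.6 | 90 | 27.4 |
| 150 | 32.6 | 90 | 57.4 |
| 153 or more | 30 | 90 | 60 |

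The gap opens at g = 182.6 − 90 = 92.6 days and is complete at g = 182.6 − 30 = 152.6 days.

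The protocol allows such a sequence. Table 15 stops cetuximab permanently for a Grade 3 or 4 infusion reaction. Section 6.5.3 provides for study visits after cetuximab is discontinued. Section 6.5.4 ends all treatment only when an agent cannot be tolerated with at least one other.

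The joining word in 10.4 is *and*, with no later-of rule. If both limits had to be met, reporting for a man who stopped everything together would end at day 30 against a window ending at day 182.6, leaving 182.6 − 30 = 152.6 days uncovered.

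**2. LVEF**

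Inputs: 16 weeks (Table 14) and 30 days after the last dose of study drug (Section 10.2.3). Assumption: the 16 weeks run from the last binimetinib dose; Table 14 does not state the start.

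- 16 × 7 = 112 days.
- If all drugs stop together, 112 − 30 = 82 days fall after the 30-day limit.
- If another study drug continues for *d* days after binimetinib, the shortfall is max(0, 82 − d). It is gone once d reaches 82.

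This counts the 30-day limit only. Section 10.2.3 also releases an event once it stabilises, whereas the LVEF rows end only at resolution or 16 weeks.

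**3. Non-retinal eye events**

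Both texts stop at stabilisation or resolution. They differ only for an event still unstable at day 30: Table 14 continues and 10.2.3 does not require it. No length can be calculated.

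**The case against.** The strongest objection is that Section 10 does not close safety collection at day 30. Related SAEs are captured afterwards without a time limit, and SAP Section 15.2 counts new ones as treatment-emergent. Ongoing related events may be followed longer. Section 10.1.1 has abnormal laboratory, vital-sign and ECG results that qualify as AEs repeated until normal or stable, and Section 8.3.5.1 says the same of ECGs. A significant eye abnormality at end of treatment triggers a full ophthalmic examination at the 30-day visit. All of this stands, so the cardiac conflict is confined to LVEF and the eye conflict to unstable non-retinal events.

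Stronger readings that a reader might infer, and why the documents do not support them:

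- *Partner pregnancies at days 31 to 90 generally go unreported.* The cetuximab clause covers those days unless cetuximab stopped well before the oral drugs.
- *Reporting stops at the earlier limit for every man.* The wording permits this reading but does not compel it. Read as alternatives, the two limits equal the female contraception windows in 5.3.1, which suggests separate limits for each drug were meant.
- *Long gaps between the drugs are common, because median time on treatment was 7.9 months.* That figure is total time on treatment in another trial's safety lead-in. It says nothing about how far apart the drugs stop.
- *LVEF follow-up is always 82 days short.* Section 6.5.4 lets a subject who stops binimetinib for an AE continue the other two drugs. AE follow-up and scheduled ECHO/MUGA then continue.
- *Late skin tumours and other malignancies are wrongly left out.* The 6-month surveillance is a recommendation, and a 30-day AE window with later related SAEs is applied consistently. A late case judged serious and related is still captured. Asking for the rest is a preference, not a correction.

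**Conclusion.** Two mismatches hold.

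1. The 30-day oral-drug limit for partner-pregnancy reporting is 60 days shorter than the male contraception limit for the same drugs. With the reporting limits read as alternatives, this matters only when cetuximab stopped more than about 92 days before the oral drugs, and fully only from about 153 days. The documents give no frequency, so the number of men affected cannot be estimated. The ambiguity of the joining word is a separate reason to reword.

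2. The 30-day limit in 10.2.3 conflicts with Table 14 for LVEF and for non-retinal eye events still unstable at day 30. For LVEF, up to 82 days of monitoring lie beyond that limit if all drugs stop on one day and the 16 weeks start with the last binimetinib dose; less, or none, if other drugs continue.

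Late events in these situations could be missed or recorded at the investigator's discretion. The documents do not show that they would be. Neither point affects the primary response analysis.

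**What to change.** - **Section 10.4:** word the partner-pregnancy reporting window to equal the male contraception window already in Section 5.3.1, with an explicit later-of rule in place of the bare *and*. This removes the gap for every value of g. It takes the 5.3.1 window as it stands and does not judge its length.
- **Section 10.2.3:** reconcile with Table 14 so that, where Table 14 gives a related event a longer monitoring period, its outcome is recorded for that period. State when the 16 weeks start. This concerns data recording; which monitoring period is appropriate is for the sponsor to settle.
- **Optional:** record KA, SCC and other new malignancies found in the recommended 6-month surveillance, whatever their seriousness or causality. The 3-monthly survival contacts would not be enough: they end at End of Study, which is reached once all treated subjects have progressed or discontinued, including the 30-day visit (Sections 9.2.5.2 and 15.3.1). The last subjects would need another route.

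The first two changes are protocol wording. Their cost is slightly more late safety data to process. The optional item would cost more, because it needs collection beyond the current End of Study for some subjects.

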10.5. SPONSOR'S RESPONSIBILITIES FOR SAFETY REGULATORY REPORTING PURPOSES

The Sponsor and/or designee will submit expedited and periodic reports to both Competent Authorities and Ethics Committees as regards to the Directive 2001/20/EC EU regulations or as per local specific regulatory requirements in participating countries.

11. DATA COLLECTION AND STUDY MONITORING

11.1. DATA COLLECTION

11.1.1. Case Report Forms

An e-CRF will be provided by the CRO. It will contain fields for all the data required to be obtained based on the protocol, except any computerized data which will be directly transferred to the database.

The Investigator is responsible for ensuring that all required data are properly recorded in each subject's e-CRF and related documents. Prior to the start of the study, the Investigator will complete a delegation form. The signature and initials of all persons in charge of e-CRF completion should be recorded on this form.

The e-CRFs are to be completed in a timely manner and preferably within 3 days of the study visit, allowing extraction of appropriate e-CRF data available for Sponsor review. All the information will be recorded from source documents into the e-CRF by an authorized person.

All answer fields in the e-CRF pages must be filled in for all visits, otherwise an explanation should be given.

The completed e-CRF, including any paper SAE/pregnancy/pregnancy outcome forms, must be promptly reviewed, signed and dated by a qualified person, who is an Investigator.

Each subject who will have received the study treatment must be entered into the e-CRF.

For all other subjects having signed an ICF, the subject's summary page of the e-CRF, along with all applicable information documenting the screen failure/discontinuation reason must be completed.

The Investigator is responsible for the management, completeness and accuracy of the information in the e-CRF. The CRAs will be trained about the e-CRF and have access to the e-CRF module for monitoring purposes.

A copy of the e-CRF with all related documentation will be stored by the Sponsor at the end of the study. Another copy of the e-CRF data will be stored by the Investigator for at least 25 years or according to the local requirements.

11.1.2. Source Documents

A source document is an original record or certified copy of an original record of clinical findings, observations or any other medical or paramedical activities performed during the clinical trial, necessary for the transcription and the verification of the collected data.

Source documents along with all other trial-related documents (copies of all ICFs, e-CRFs, treatment inventories and any correspondence related to the study) must be kept in the Investigator's file throughout the study, and then must be stored in the study center's archives for a period of at least 25 years or as per local legal requirements.

For further details see **Section 15.2**

11.2. STUDY MONITORING

11.2.1. Monitoring visits

On-site visits will be carried out by a representative of the Sponsor's staff (Study Manager or CRA) prior to study initiation and at regular intervals to closely monitor the study throughout its duration. Additional visits and communication by telephone, mail, email, fax or meeting may be performed if necessary. Any site visit performed by the Sponsor's representatives will be recorded in the Investigator's site file.

11.2.1.1. Site Preselection Visit

Before selecting a center for the study, a visit will be carried out by the CRA and/or the Study Manager to ensure that the Investigator has the necessary capacities (availability subject, recruitment, environment), technical means and staff to carry out the study.

11.2.1.2. Initiation Visit

Before the start of the study at all investigational sites, an initiation visit will be carried out by the CRA to check at a minimum that:

- The Investigator:
 - has received the technical protocol, administrative and financial agreement signed by all parties
 - has received the written statement of the IEC/IRB approval and the list of its members and their functions
 - has received the written statement of Competent Authority approval
- The original dated and signed *curriculum vitae* of the Investigator(s) has been collected
- Laboratory normal ranges have been collected
- All study materials are available on the study site
- All participants agree with the monitoring procedures and know the study procedures
- All participants are aware of a possible audit or inspection

The CRA also has to provide training on the study protocol requirements and study specific procedures.

11.2.1.3. Follow-up Visits

Throughout the study, regular follow-up visits will be carried out by the CRA to check compliance with GCP, strict application of the protocol, subject's informed consents, proper retention, storage and management of the study treatment, as well as the source and other trial-related documents. It is the CRA's responsibility to inspect e-CRFs at regular intervals throughout the study to verify the completeness, accuracy and consistency of the data, to verify the conformity of the data entered into the e-CRF with the source documents and to ensure its correct completion, and AE reporting.

11.2.1.4. Closing Visit

At the end of the study, a final visit will be carried out by the CRA to:

- Verify that the copies of e-CRFs are correctly stored
- Control the accountability of intact and used treatment units before destruction
- Obtain the last data clarifications and/or solutions if any
- Make an on-site review of all study documentation and complete it if necessary
- Remind the Investigator of his/her regulatory obligations, study document archiving process and duration.

11.2.2. Direct Access to Source Documents

In accordance to the requirements of GCP, all Sponsor representatives (Study Manager, CRA and Auditors) must be given direct access to all source and study data to perform quality monitoring/audit, thus ensuring accuracy and completeness of data.

Investigators are reminded that all Sponsor representatives maintain professional confidentiality with regards to the subject data.

11.3. PERIODIC SAFETY DATA REVIEW

All safety data collected from the study (SAEs, AEs, clinical laboratory data, vital signs, physical examinations, ophthalmic examinations, dermatologic examinations, tumor assessments, ECG, ECHO/MUGA scans, etc.) are periodically reviewed by the medical monitor or designee to detect any potential safety signals during the study and to review safety critical data. The modalities of this safety signal detection review is described in a separate document.

11.4. STEERING COMMITTEE

A steering committee (SC) will be established comprising Investigators participating in the trial and Sponsors' representatives from the Clinical Study Team.

The SC will ensure transparent management of the study according to the protocol through recommending and approving modifications as circumstances require. The SC will be responsible for reviewing the safety data of the subjects treated in the study as well as reviewing efficacy results for ORR from the interim and final analyses.

The SC will review protocol amendments as appropriate. The details of the role of the Steering Committee will be defined in a SC charter.

